Inclusion criteria: all subsequent patients undergoing surgery that expectedly will be treated and observed in hospital for more than 24 hours postoperatively. Exclusion criteria: patients < 18 years of age, refusal of participation, poor communication capabilities and surgery performed that is not compatible with anticipated mobilization during the first 24 postoperative hours.

Primary and secondary endpoints

Primary endpoint of this study will be time to full mobilization of the patient, defined as being able to walk more than one step with/without support. Secondary endpoints will be clinically significant reduction (more than 23% [16]) in measured pain evaluated by a 0-10 scale (Verbal Numeric Rating Scale), significant changes in doses (OMEQ) of postoperative administered opioids, re-admissions to the recovery unit, significant increased patient satisfaction of treatment given and reduction in length of hospital stay.

Methods of analysis

Descriptive statistics will be used to compare baseline characteristics between groups, such as type of surgery, type of anaesthesia, regular pain medication, age, relevant comorbidity (Charlson Comorbidity Index), ASA-classification and body mass index. The effect of ESS on the primary outcome (time to mobilization) will be analysed by Kaplan-Meier estimators, and we will also use Cox-regression analysis to adjust for baseline covariates. For the secondary outcomes, we will use linear and logistic regression to estimate differences in means or odds ratios between study groups, depending on the measurement scale. Non-normally distributed variables will be log transformed, or analysed using non-parametric tests. The precision of all estimated effects will be given by a 95% confidence interval. Due to the anticipated positive influence from the ESS group on

postoperative treatment to the SCG, we will also see if there is a progression in eventually differences in the endpoints between the SCG and ESS group.

Sample size

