We performed a power analysis based on the sub-group results of a validation study addressing ESS in total 207 patients [11]. Estimates shows that for obtaining a power of 0,8 with alpha cut-off at 0,05 and beta cut-off at 0,2, a sample size of total 130 patients was required to reach a 25% reduction of time until full mobilization (being able to walk one or more steps with/without support). A total sample size of 130 patients was required to reach a 25% reduction in total hospital stay and a total sample size of 506 and 176 patients was required to reach a 25% reduction in pain at rest and at mobilization, respectively. (Kane SP. SampleSizeCalculator. <http://clincalc.com/Stats/SampleSize.aspx>). Except from pain at rest, which is of limited interest in this study, these sample size calculations suggest that a total sample size of 200 (100 in each group) will be sufficient to detect any meaningful effects of the intervention on both primary and secondary outcomes.

Data collection

Patients will be included after giving their informed signed consent. In both groups, a standardized questionnaire (see attachment) focused on postoperative management and satisfaction will be performed 24 hours postoperatively. In group ESS, we will register ESS for the first 24 hours postoperatively. Registration of ESS is to be done hourly for the first four hours, and then every second hour after the patient has arrived to the ward. For all patients the Modified Aldrete Score and the New Early Warning Score [14-16] will be performed for comparison. If ESS>10 in patients of group ESS, the anaesthesiologist on duty might be called upon (not involved in the study) for assistance. He/she will afterwards be asked to evaluate the necessity of the consultation for later sensitivity/specifity test. All the data will be collected by the nurses with the help of a designed program (Patient Status Engine) on tablet PC from Isansys (Isansys Lifecare Ltd., Oxfordshire, UK) that incorporates ESS into their wireless monitoring platform, Patient Status Engine (PSE) which is a CE-approved device (class IIa) designed for use in hospital settings to collect vital parameters. The data is then transferred to a protected data base locally. Statistical analysis will be performed in SPSS.

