Reg.nr ClinicalTrials.gov: NCT03438578.

Tables

[figure not shown]
Table 1 Description of Efficacy Safety Score (ESS)

Mental status	Score
Awake and alert patient	0

Awake patient, but influenced by drugs. Difficulties in communication.	5
Acutely confused, upset/uneasy, hallucinated or euphoric patient	10
Unresponsive patient	15*
Postoperative nausea and vomiting (PONV) status	
No postoperative nausea or vomiting	0
Postoperative nausea only	5
Postoperative nausea and vomiting/retching	10
Pain status at rest	
No postoperative pain	0
Low intensity postoperative pain (VNRS 1-3)	1-3
Moderate intensity postoperative pain (VNRS 4-6)	4-6
Severe intensity postoperative pain (VNRS 7-10)	7-10
Pain status during movement	
No postoperative pain	0
Low intensity postoperative pain (VNRS 1-3)	1-3
Moderate intensity postoperative pain (VNRS 4-6)	4-6
Severe intensity postoperative pain (VNRS 7-10)	7-10
General condition status	
No remarks	0
Minor discomfort (e.g. light-headedness, minor itching, blurred vision, decreased urination etc.)	5
Excessive discomfort (e.g. severe dizziness, itching, restlessness, urine retention, sensation of cold/warmth, cold sweating)	10
Acute circulatory abnormalities (blood pressure \leq 80 or \geq 200mmHg, heart rate \leq 40 or $>$ 110)	15*
Acute respiratory abnormalities (dyspnoea, respiration rate $<$ 9 or $>$ 20/min, long pauses in breathing, shallow breathing)	15*

***Any single score of 15 (on either consciousness, circulation or respiration) should call for IMMEDIATE activation of acute assistance with the patient.**

Flowchart of phases in Efficacy Safety Score study, St Olavs Hospital HF, Orkdal B3:

References

1. Le Manach, Y., et al., *Preoperative Score to Predict Postoperative Mortality (POSPOM): Derivation and Validation*. Anesthesiology, 2016. **124**(3): p. 570-9.
2. Maier, C., et al., *The quality of pain management in German hospitals*. Dtsch Arztebl Int, 2010. **107**(36): p. 607-14.
3. Dolin, S.J. and J.N. Cashman, *Tolerability of acute postoperative pain management: nausea, vomiting, sedation, pruritus, and urinary retention. Evidence from published data*. Br J Anaesth, 2005. **95**(5): p. 584-91.
4. Benjamin (22) died after bone fracture, in VG. 2011: <http://www.vg.no/helse/odelagt-i-helsevesenet/artikkelen.php?artid=10093729> (01.12.2015).
5. Got to strong medications - Davoud (23) died, in Nettavisen. 2011: <http://www.nettavisen.no/nyheter/article3257721.ece> (01.12.2015).

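### The necessity ratings cover only called consultations at ESS>10, so they can give a positive predictive value but neither the sensitivity nor the specificity of that cut-off

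*Combined protocol and SAP*

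**What the plan says.** All the relevant rules are in the Data collection section of the combined protocol and SAP, apart from one in Table 1.

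- **Who is scored.** "In group ESS, we will register ESS for the first 24 hours postoperatively". The schedule is: "Registration of ESS is to be done hourly for the first four hours, and then every second hour". No ESS recording is described for the standard care group.
- **When a consultation happens.** "If ESS>10 in patients of group ESS, the anaesthesiologist on duty might be called upon (not involved in the study) for assistance". The call is therefore permitted, not required.
- **What is rated, and why.** "He/she will afterwards be asked to evaluate the necessity of the consultation for later sensitivity/specifity test". No cut-off is named for this test; ESS>10 is the only threshold in that section.
- **Another trigger for assistance.** The note to Table 1 reads: "Any single score of 15 (on either consciousness, circulation or respiration) should call for IMMEDIATE activation of acute assistance with the patient". The text does not say that this assistance is rated for necessity.
- **Other scores.** "For all patients the Modified Aldrete Score and the New Early Warning Score [14-16] will be performed for comparison".

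Methods of analysis does not mention the test. For secondary outcomes it says "For the secondary outcomes, we will use linear and logistic regression to estimate differences in means or odds ratios between study groups", which concerns the randomised comparison and not diagnostic accuracy. The test is not among the primary and secondary endpoints.

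**The concern.** Sensitivity needs the number of patients in need whom the score missed. Specificity needs the number not in need whom the score correctly left alone. Both counts lie among readings of 10 or below, and the text describes no necessity rating there. The rating is attached to a consultation, and the consultation to a high score, so the reference standard is applied only to test-positive cases, and only to those for which someone was called.

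At stake is the meaning of a possible later claim. The Research questions and goals section presents the project as a contribution to validating ESS and hopes to identify patients who need closer care. A sensitivity at or near 100% would be read as showing that ESS>10 overlooks no such patient. These ratings cannot show that, whatever they turn out to be.

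**Working it through.** The plan states no sensitivity, specificity or sample size for this test, so there is no figure to reproduce. The check asks which cells of the two-by-two table the described ratings can fill.

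**1. What is observed**

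| Reading | Necessity rating described? | Cells |
|---|---|---|
| ESS>10, anaesthesiologist called | Yes | true positives (TP), false positives (FP) |
| ESS>10, not called | No | TP or FP, unknown |
| ESS of 10 or below | No | false negatives (FN), true negatives (TN), unknown |

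The Table 1 trigger adds nothing to the last row: if ESS is the sum of its items, a single item of 15 already puts the total above 10.

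**2. Rated cases taken alone**

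Sensitivity = TP/(TP+FN), specificity = TN/(TN+FP), positive predictive value (PPV) = TP/(TP+FP). With no low score rated, FN and TN are both empty:

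- sensitivity = TP/(TP+0) = 100%
- specificity = 0/(0+FP) = 0%

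This holds for any mix of ratings. Only the PPV carries information.

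**3. How much the unrated low scores matter**

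The schedule gives 4 hourly readings plus 10 two-hourly ones (hours 6 to 24), so about 14 per patient and at most 14 × 100 = 1,400 in the ESS group. The documents do not give the share above 10 or the share judged necessary, so the cells below are assumptions. Per 1,000 readings take 260 above 10, all called, with 80 judged necessary and 180 not, and 740 unrated low scores. PPV = 80/260 = 30.8% in every row.

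| Low scores that needed help | Sensitivity | Specificity |
|---|---|---|
| 0 | 80/80 = 100% | 740/920 = 80.4% |
| 20 | 80/100 = 80% | 720/900 = 80.0% |
| 80 | 80/160 = 50% | 660/840 = 78.6% |
| 740 (logical limit) | 80/820 = 9.8% | 0/180 = 0% |

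The first row is what results from counting every unrated low score as a true negative. The recorded ratings are identical in all four rows.

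A second assumed set leads to the same conclusion. Of 1,400 readings, 140 are above 10, all called, 112 judged necessary and 28 not, leaving 1,260 low scores. If 0%, 1%, 2% or 5% of the low scores needed help (0, 12.6, 25.2 or 63 readings), sensitivity is 112/112 = 100%, 112/124.6 = 89.9%, 112/137.2 = 81.6% or 112/175 = 64.0%. Specificity stays between 1,260/1,288 = 97.8% and 1,197/1,225 = 97.7%.

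**4. The optional call**

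In the first set, suppose half of the 260 are called: 40 rated necessary, 90 not, 130 unrated. With nothing assumed about the unrated readings:

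- sensitivity runs from 40/(40+740) = 5.1% to 100%
- specificity runs from 0% to 740/(740+90) = 89.2%
- PPV among called consultations is still 40/130 = 30.8%, but the share necessary among all 260 high readings could be anything from 40/260 = 15.4% to (40+130)/260 = 65.4%

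The estimable PPV is therefore that of a called ESS>10, and the share called has to be known to interpret it.

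**5. Comparisons within the rated cases**

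Suppose a higher cut-off keeps 60 of the 80 necessary and 70 of the 180 unnecessary calls. Conditional on a called ESS>10, its sensitivity is 60/80 = 75% and its specificity 110/180 = 61.1%. With all high readings called, its own sensitivity is 60/80 = 75%, 60/100 = 60% or 60/160 = 37.5% when 0, 20 or 80 needs were missed. The conditional comparison is valid if labelled as such; the unconditional figure is not available.

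**The case against.** The strongest reply is that the harm needs a step nobody has announced. The rated-only table that gives 100% sensitivity also gives 0% specificity, which any reader would see is degenerate. A misleading result appears only if unrated low scores are counted as true negatives, and no section says they will be. This stands. A reader might infer that the trial is set to publish a sensitivity of 100%; the documents do not support that. They support only that the ratings cannot deliver the test.

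Further objections:

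- **Other data exist at low scores.** The Aldrete and early warning scores are taken on all patients, and telemetric variables run in parallel in the ESS group. ESS could be compared with these, but they are not necessity ratings, and the plan ties the test to the rating. Agreement with another score is a different question.
- **No cut-off is named, and the test is described as later.** A different threshold, or a separate specification, may be intended. For a higher cut-off the ratings give only the conditional quantities in step 5, and a later specification cannot supply ratings that were not made at the time.
- **Specificity looks safe.** In the illustrations it moves little when every high score is called and need is rare at low scores. That comes from the assumed cells. True negatives are unobserved, so specificity is not identified either.
- **The cells are invented.** They are. The floors of 9.8% and 5.1% require every low score to hide a need and are logical limits, not forecasts. The illustration also counts readings, whereas one consultation may cover several. The structural result in step 2 needs none of these numbers.
- **The flow-chart was not readable.** Study design refers to an enclosed chart whose content is missing from the text read. If it describes ratings at low scores, the point falls.

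**Conclusion.** The sentence is wrong as written, and the point is minor. From the ratings the text describes, neither the sensitivity nor the specificity of ESS>10 is identified. What can be estimated is the PPV among called ESS>10 consultations, together with comparisons labelled as conditional on such a call. In the assumed examples the same ratings are compatible with sensitivities from 100% down to 50%, or down to 64%, under moderate rates of missed need; those figures show the size of the gap and do not predict this trial.

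A reader might infer that the problem reaches the trial's main results. It does not: the test is outside the listed endpoints and the planned analyses, and no between-group comparison uses these ratings.

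The conclusion rests on two conditions: that the flow-chart adds no ratings at low scores, and that ESS is the sum of its items, so that the Table 1 trigger creates no consultations at a total of 10 or below.

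**What to change.** In Data collection, replace the closing phrase that names the sensitivity/specificity test with:

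*to estimate the share of called ESS>10 consultations judged necessary (positive predictive value, 95% CI clustered by patient). The share of ESS>10 episodes that led to a call will be reported. No sensitivity or specificity of the ESS>10 cut-off will be claimed from these ratings. Any comparison with higher cut-offs or other scores will be labelled as conditional on a called ESS>10.*

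For each ESS>10 reading, record whether a call was made. Group consecutive high readings covered by one consultation into one episode, so that a single rating is not counted several times.

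The cost is a few lines of text, one yes/no field per high reading and an episode number; the documents describe no call log at present. The trigger, the call and patient care are unchanged. The downside is that the trial will not report how many patients in need ESS misses.

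Rating a sample of low readings afterwards, to rescue sensitivity, is not proposed. It needs extra raters, and it would combine the called doctor's judgement for high scores with a different reference standard for low ones (differential verification).

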Attachment 1:

MAL FOR INTERVJU 1. POSTOPERATIVE DAG

Efficacy Safety Score

Prosjekt nr: _____

Informert samtykke (sett kryss):

Inngrep: _____

Operasjonsdato: _____

1. **Tidspunkt for mobilisering (gå ett eller flere skritt med/uten støtte):** kl _____

2. **Kan du angi verste smerte siden operasjonen (0-10)?** _____

• Hvilken situasjon utløste verste smerte: _____

3. **Kan du angi gjennomsnittlig smerte siden operasjonen (0-10):** _____

4. **Har du opplevd kvalme etter operasjonen?** Ja/Nei

• Hvis Ja, hvor stor andel av tiden: En episode - litt - halvparten - meste - hele tiden

5. **Har du hatt brekninger og/eller oppkast etter operasjonen?** Ja/Nei

6. **Kan du si noe om nattesøvnen etter operasjonen:**

• Mengde: Ingen – redusert – normal – øket – kraftig øket

• Kvalitet: Normal – urolig/mareritt – urolig/smerte – urolig/vonde tanker

7. **Kan du angi eventuell bekymring/engstelse før operasjonen:**

• Ingen – litt – middels – mye – svært mye

8. **Kan du angi eventuell bekymring/engstelse nå etter operasjonen:**

• Ingen – litt – middels – mye – svært mye

9. **Kan du si noe om din følelse av sikkerhet og trygghet etter operasjonen:**

• Sikker og trygg – stort sett sikker/trygg – verken eller - noe usikker/uttrygg – usikker/uttrygg

10. **Kan du angi din evne til å huske, resonnere, ta beslutninger eller følge med etter operasjonen:**

• Normal - litt redusert – redusert - en del redusert - kraftig redusert

11. **Andre plager eller bivirkninger etter operasjonen?** _____

12. **Kan du angi din grad av tilfredshet med behandling etter operasjonen:**

• Meget utilfreds – litt utilfreds – nøytral – tilfreds – meget tilfreds

13. **Eventuelt andre kommentarer/tilbakemeldinger:**

Attachment 2:

“Introducing novel clinical tools in postoperative treatment at the ward. Effects on working situation for care providers, patient safety and quality of care”

Study protocol (Tentative draft)

The overall objective of the study is to generate new knowledge and strengthen the decision-making basis for how new tools and technical innovations are to be introduced in clinical hospital practice. Focus is on how postoperative care providers respond to new checklists and patient monitoring in everyday work; how novel tools might influence on the healthcare professionals' clinical work and if this has an effect on patient safety and experienced quality of care.

The basis for this is the project conducted at St Olavs Hospital, Orkdal ward B3 in 2018:

“Postoperative treatment with Efficacy Safety Score and wireless patient monitoring system at a general ward: a prospective randomized controlled study.”

The study seeks to highlight the following factors related to the use of Efficacy Safety Score (ESS) by doctors and nurses:

- Functionality
 - Which technical functionality is available to respondents – and how this affects the clinical postoperative setting? Including: Right information to the right recipient?
 - Valuable information in daily clinical work?
 - Support for holistic postoperative care as part of standardized patient pathways?
- Use
 - To what extent does the staff use the information from this system? Does information gathered with ESS provide better patient care as judged by the staff?
 - Does use of ESS promote self-confidence and knowledge for healthcare professionals in clinical settings?
 - Does use of ESS improve inter-disciplinary communication?
 - To what extent are respondents satisfied with the functionality of the ESS?
 - Technical implementation and technical support – to what extent are these barriers for new clinical tools?

Methods

As a background we will perform a thorough search in peer-reviewed published academic works about identified pit-falls and success actors when introducing new tools/techniques for clinical medical settings. This will be a broad approach to identify obstacles to routine changes and limiting factors in external and internal education/support among staffing.

The project will plan and conduct a survey on the use and experience of the integrated ESS monitoring among doctors and nurses at St Olavs Hospital, Orkdal ward 3. The study is based methodically on questionnaires that will be developed for this purpose. Questionnaires will include research-oriented issues that are thematically linked to the introduction, management and implementation of clinical innovations. We will seek assistance to development of questionnaires

from NTNU and other available contributors at St Olavs Hospital with focus on nursing and innovation.

Recruitment of respondents will take place at St. Olav Hospital, Orkdal ward 3. The target group for the survey is nurses and doctors in clinical work who have been working there during the project started in 2018. The survey will be available electronically for recruited respondents and answered anonymously through Questback. Age, gender, years of employment and clinical specialization will be demographic variables to be analyzed with the findings in the questionnaires.

The study is planned published in international medical journals with focus on overall system improvement and quality of care.
